7.7.2.1 Imaging Restriction and Precautions

It is the local imaging facility's responsibility to determine, based on participant attributes (eg, allergy history, diabetic history, and renal status), the appropriate imaging modality and contrast regimen per imaging study. Imaging contraindications and contrast risks are to be considered in this assessment. Renal function should be assessed in study participants receiving gadolinium-based contrast agent with regard to contrast agent dose and appropriateness of any administered contrast agent. Specific to MRI, participants with severe renal insufficiency, defined as estimated glomerular filtration rate (eGFR) < 30 mL/min based on the Cockcroft-Gault formula²⁰ (Appendix 5), are excluded from the study. In addition, participants may be excluded from MRI and study participation in Part B if they have tattoos, non-MRI compatible metallic implants, pacemakers, etc. This will be outlined in the Imaging Manual. A local safety read of the MRI should be performed and shared with the investigator.

Gentle hydration before and after IV contrast should follow local standard of care. The ultimate decision to perform MRI in an individual participant in this study rests with the site radiologist, the investigator, and standards set by the local Ethics Committee.

7.8 Continued Access to Study Intervention after the End of the Study

At the end of the study, BMS will not continue to provide BMS-supplied study intervention to participants/investigators. The investigator should ensure that any patient with MS receives appropriate standard of care to treat the condition under study.

BMS reserves the right to terminate access to BMS-supplied study intervention if any of the following occur: a) the study is terminated due to safety concerns; b) the development of ¹¹C-BMS-986196 is terminated for other reasons, including, but not limited to not meeting the study objectives. In all cases, BMS will follow local regulations.

8 DISCONTINUATION CRITERIA

8.1 Discontinuation from Study Intervention

Participants MUST discontinue IP (and Non-IP/AxMP at the discretion of the investigator) for any of the following reasons:

- Participant's request to stop study intervention. Participants who request to discontinue study intervention will remain in the study and must continue to be followed for protocol-specified follow-up procedures. The only exception to this is when a participant specifically withdraws consent for any further contact with him/her or persons previously authorized by the participant to provide this information
- Any clinical AE, laboratory abnormality, or intercurrent illness which, in the opinion of the investigator, indicates that continued participation in the study is not in the best interest of the participant
- Termination of the study by BMS
- Loss of ability to freely provide consent through imprisonment or involuntarily incarceration for treatment of either a psychiatric or physical (eg, infectious disease) illness. (Note: Under specific circumstances and only in countries where local regulations permit, a participant who has been imprisoned may be permitted to continue as a participant. Strict conditions apply, and BMS approval is required.)
- Pregnancy (study treatment must be discontinued immediately. Refer to Section 9.2.5).
- Significant noncompliance with protocol (eg, procedures, assessments, medications, etc). The investigator should discuss such issues with the medical monitor.
- Abnormal liver tests suggestive of potential drug-induced liver injury (DILI) as defined in Section 9.2.7.
- A participant has reported an adverse event meeting the stopping rule defined in Section 8.4.
- A participant has experienced a protocol-defined MS relapse after administration of ¹¹C-BMS-986196 at the Day 1 Visit.

Refer to the Schedule of Activities for data to be collected at the time of treatment discontinuation, follow up, and for any further evaluations that can be completed.

All participants who discontinue study intervention should comply with protocol-specified follow-up procedures as outlined in Section 2. The only exception to this requirement is when a participant withdraws consent for all study procedures, including post-treatment study follow-up, or loses the ability to consent freely (eg, is imprisoned or involuntarily incarcerated for the treatment of either a psychiatric or physical illness).

If study intervention is discontinued prior to the participant's completion of the study, the reason for the discontinuation must be documented in the participant's medical records per local regulatory requirements in each region/country and entered on the appropriate CRF page.

8.1.1 Post-study Intervention Study Follow-up

Participants who discontinue study intervention may continue to be followed.

Protocol Amendment No.: 05

8.2 Discontinuation from the Study

Participants who request to discontinue study intervention will remain in the study and must continue to be followed for protocol-specified follow-up procedures. The only exception to this is when a participant specifically withdraws consent for any further contact with him/her or persons previously authorized by participant to provide this information.

- Participants should notify the investigator of the decision to withdraw consent from future follow-up.
- The withdrawal of consent should be explained in detail in the medical records by the investigator, as to whether the withdrawal is from further treatment with study intervention only or also from study procedures and/or post-treatment study follow-up, and entered on the appropriate CRF page.
- In the event that vital status (whether the participant is alive or dead) is being measured, publicly available information should be used to determine vital status only as appropriately directed in accordance with local law.
- If the participant withdraws consent for disclosure of future information, the Sponsor may retain and continue to use any data collected before such a withdrawal of consent.

8.2.1 Individual Discontinuation Criteria

- A participant may withdraw completely from the study at any time at his/her own request, or may be withdrawn at any time at the discretion of the investigator for safety, behavioral, compliance, or administrative reasons. This is expected to be uncommon.
- At the time of discontinuing from the study, if possible, an early termination visit should be conducted, as shown in the Schedule of Activities. See the Schedule of Activities for data to be collected at the time of study discontinuation and follow-up and for any further evaluations that need to be completed.
- The participant will be permanently discontinued both from the study intervention and from the study at that time.
- If the participant withdraws consent for disclosure of future information, the Sponsor may retain and continue to use any data collected before such a withdrawal of consent.

8.3 Lost to Follow-up

The following actions must be taken if a participant fails to return to the clinic for a required study visit:

- All reasonable efforts must be made to locate participants to determine and report their ongoing status. This includes follow-up with persons authorized by the participant.
- Lost to follow-up is defined by the inability to reach the participant after a minimum of **three (3)** documented phone calls, faxes, or emails, as well as lack of response by participant to one (1) registered mail letter. All attempts should be documented in the participant's medical records.

• If it is determined that the participant has died, the site will use permissible local methods to obtain date and cause of death.

- If the investigator's use of third-party representative to assist in the follow-up portion of the study has been included in the participant's informed consent, then the investigator may use a Sponsor-retained third-party representative to assist site staff with obtaining the participant's contact information or other public vital status data necessary to complete the follow-up portion of the study.
- The site staff and representative will consult publicly available sources, such as public health registries and databases, in order to obtain updated contact information.
- If, after all attempts, the participant remains lost to follow-up, then the last known alive date as determined by the investigator should be reported and documented in the participant's medical records.

8.4 AE-defined Stopping Rules

AE-based stopping rules are triggered if an AE of sufficient significance (as judged by the investigator) warrants halting further enrollment and tracer administration. The AE must be considered related to study treatment and must not be an underlying condition of the study participant.

In addition, the following criteria trigger stopping rules:

- One participant experiences a serious adverse event (SAE) that is considered related to ¹¹C-BMS-986196 or BMS-986196.
- Two participants experience severe AEs that are related to ¹¹C-BMS-986196 or BMS-986196.

If either above listed criteria for stopping rules are met, a review of the safety data will be initiated to assess if the initial assessment of the relevant safety events was accurate.

If the review of the safety data concludes that the stopping rules were not met, then a justification for study restart will be submitted to the IEC/IRB and the study will only restart after IEC/IRB approval for restart has been obtained. If review of the safety data concludes that the stopping rules were met, the study will only restart after submission of a substantial amendment providing the data and justification for the restart.

9 STUDY ASSESSMENTS AND PROCEDURES

- Study procedures and timing are summarized in the Schedule of Activities (Section 2).
- Protocol waivers or exemptions are not allowed in this study.
- All safety concerns must be discussed with the medical monitor immediately upon occurrence or awareness to determine if the participant should continue or discontinue treatment.
- Adherence to the study design requirements, including those specified in the Schedule of Activities (Section 2), is essential and required for study conduct.
- All screening evaluations must be completed and reviewed to confirm that potential participants meet all eligibility criteria before enrollment and tracer administration.

9.1 Efficacy Assessments

Not applicable; efficacy will not be assessed in this study.

9.1.1 Imaging Assessments

9.1.1.1 PET Assessments

PET procedures will be conducted at the PET center at each site. Female participants will be given a pregnancy test prior to the initiation of any imaging procedures. If the test is positive, the scans will not be conducted.

Participant preparation for PET scanning consists of placement of venous lines and placement of arterial lines. In Part C, no arterial lines will be placed. IV line placement will be performed by the research nurse, certified nuclear medicine technologist, or investigator. The arterial and venous catheters will be placed by experienced staff, before the PET scan. One IV line will be used for tracer administration. The arterial line and, if applicable, a second IV line will be used to draw arterial and venous blood samples, respectively, for metabolite analysis and for determination of the fraction of plasma radioactivity unbound to protein.

The goal of arterial and venous lines is to be able to measure absolute physiological functions by mathematically relating the signal (from the PET scanner) to the tracer availability (from the blood). This approach provides the gold-standard data. If an arterial line cannot be placed, a second IV line may be placed for IV blood sampling. IV blood sampling should occur on the arm opposite of the arm used for ¹¹C-BMS-986196 tracer administration. All processing of blood samples for ¹¹C-BMS-986196 input function determination should occur promptly at the PET center due to the short half-life of C-11 (20 min).

PET scans will be performed and acquired as participants lie supine on the scanner bed.

For each PET scan, approximately 370 MBq (10 mCi) of ¹¹C-BMS-986196 will be administered by a slow IV bolus. Acquisition of emission data will begin shortly after administration and continue for a period of up to 120 minutes. Vital signs (blood pressure, heart rate, respiration rate, and body temperature) will be obtained before ¹¹C-BMS-986196 administration, after completion of the PET scan procedure, and prior to discharge on each scan day. An ECG will be completed before each PET scan and prior to discharge on each scan day.

Part A

Two tracer administrations of ¹¹C-BMS-986196 are each followed by a PET scan. The interval between the first and second tracer administrations must be at least 2 hours and at most 6 days. If the second tracer administration is done on Days 5, 6, or 7, the study site staff must contact the participant remotely (ie, by phone) on Day 4 (ie, 3 days after the first PET scan) and record AEs and concomitant medications.

Before or after the first PET scan, a low-dose whole-body CT scan (from apex to upper-thigh level) will be acquired for attenuation correction. No contrast agent is administered for the CT scan.

Protocol Amendment No.: 05

Before and/or after the cranial PET scan, a low-dose cranial CT scan or MRI scan will be acquired (depending on availability of equipment). No contrast agent is administered for the CT or the MRI scan.

The maximal number of tracer administrations in Part A is 2 and the maximal number of whole-body CT scans in Part A is 1. The maximum number of cranial CT scans in Part A is 2 per cranial PET (1 before and 1 after the PET scan). Hence, the maximum number of cranial CT scans is 4 for participants who will not undergo whole-body CT scans. For all other participants in Part A, the maximum number of cranial CT scans is 2. If 2 PET scans are performed on the same day, hematology and clinical chemistry samples, VS, ECG, AEs, and review of concomitant medications are the only safety assessments that must be assessed in duplicate, and the same arterial line may be used for both scans.

If, after completion of dosimetry in Part A participants and based on emerging data from Part B, 2 additional participants are enrolled to Part A, then these 2 participants will only undergo the cranial PET scan of Visit 2, and these participants will have arterial and venous blood samples drawn during the Visit 2 PET scan. For these 2 participants, Visit 2 will be regarded as Day 1.

Part B

Two administrations of ¹¹C-BMS-986196 are each followed by a cranial PET scan. The interval between the first and second tracer administration must be at least 2 hours and at most 6 days. If the second tracer administration is done on Days 5, 6, or 7, the study site staff must contact the participant remotely (ie, by phone) on Day 4 (ie, 3 days after the first PET scan) and record AEs and concomitant medications. Participants who had a MS relapse within 30 days prior to Day 1 must start Scan 2 on Day 1 or Day 2.

Before or after each tracer administration, a low-dose cranial PET-CT or PET-MRI scan will be performed (depending on equipment availability). No contrast agent will be administered for the PET-CT scan. To account for potential significant movement during the PET scan, it is permissible to perform 1 cranial CT or MRI scan before and 1 CT or MRI scan after a cranial PET scan. At the discretion of the investigator, gadolinium-based contrast agents may be administered if a PET-MRI is performed. Participants in Part B must have at least one cranial PET-MRI scan performed with gadolinium-based contrast agent. Gadolinium-based contrast agent may be administered either at Screening or during PET-MRI.

Before a PET-MRI scan, participants will be asked for the presence of contra-indications against MRI or application of gadolinium-based contrast agents and asked to remove magnetic objects before entering the scanner.

The maximal number of tracer administrations in Part B is 3 and the maximal number of CT scans in Part B is 6. If 2 PET scan visits are performed on the same day, vital signs (VS), ECG, AEs, and review of concomitant medications are the only safety assessments that must be assessed in duplicate, and the same arterial line may be used for both scans.

In Part B, every effort must be made to perform the re-test PET scan under identical conditions as the test scan (eg, same scanning machines, same imaging procedures).

Protocol Amendment No.: 05

Date: 30-Jun-2023 72

If, based on emerging data from Part B, simultaneous sampling of venous and arterial blood sampling is considered warranted to facilitate future studies without arterial blood sampling, up to 6 participants in Part B may undergo simultaneous venous and arterial blood sampling only during one PET scan procedure. Preferably, the simultaneous and arterial blood sampling is performed during Visit 1.

Part C

Two administrations of ¹¹C-BMS-986196 will each be followed by a cranial PET scan. The second tracer administration will occur approximately 24 hours after the last administration of (unlabeled) BMS-986196.

Before or after each tracer administration, a low-dose cranial PET-CT or PET-MRI scan will be performed (depending on equipment availability). No contrast agent will be administered for the PET-CT scan. To account for potential significant movement during the PET scan, it is permissible to perform 1 cranial CT or MRI scan before and 1 CT or MRI scan after a cranial PET scan. No gadolinium-based contrast agents will be administered if a PET-MRI is performed.

Before a PET-MRI scan, participants will be asked for the presence of contraindications against MRI and asked to remove magnetic objects before entering the scanner.

The maximal number of tracer administrations in Part C is 3, and the maximal number of CT scans in Part C is 6.

In Part C, every effort must be made to perform the second PET scan under identical conditions as the first scan (eg, same scanning machine, same imaging procedures).

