6.1 Inclusion Criteria

Participants are eligible to be included in the study only if all of the following criteria apply:

1) Signed Written Informed Consent

Participants must have signed and dated an IRB/Independent Ethics Committee (IEC)-approved written ICF in accordance with regulatory, local, and institutional guidelines. This must be obtained before the performance of any protocol-related procedures that are not part of normal patient care.

2) Type of Participant and Target Disease Characteristics

For Part A and Part B:

- Body mass index (BMI) of 18 to 34 kg/m2, inclusive, and total body weight \geq 50 kg (BMI may be rounded, eg, a participant with a BMI of 34.4 would qualify).
- Documentation of normal Allen's test result at Screening and on PET scanning days in the arm that will be used for arterial line placement.

a) Part A only:

• Healthy male and female participants without clinically significant deviation from normal in medical history, physical examination (PE), ECGs, and clinical laboratory determinations

b) Part B only:

- Male or female participant diagnosed with MS according to the 2017 revisions of the McDonald diagnostic criteria 19
- EDSS score between 0 to 6.5, inclusive, at Screening

c) For Part C:

- Body mass index (BMI) of 18 to 34 kg/m^2 , inclusive, and total body weight $\geq 50 \text{ kg}$ (BMI may be rounded, eg, a participant with a BMI of 34.4 would qualify).
- Healthy male and WNOCBP participants without clinically significant deviation from normal in medical history, physical examination (PE), ECGs, and clinical laboratory determinations

3) Age of Participant

Participant must be 18 to 55 years of age, inclusive, at the time of signing the informed consent.

4) Reproductive Status

Investigators shall counsel women of childbearing potential (WOCBP) and male participants who are sexually active with WOCBP on the importance of pregnancy prevention, the implications of

Protocol Amendment No.: 05

Clinical Protocol IM038010 BMS-986196 BTKi-CNS

an unexpected pregnancy, and the potential of fetal toxicity occurring due to transmission of ¹¹C-BMS-986196 present in seminal fluid to a developing fetus, even if the participant has undergone a successful vasectomy or if the partner is pregnant.

The investigator shall evaluate the effectiveness of the contraceptive method in relationship to the first dose of tracer administration.

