## 6.3 Populations for Analyses

For analysis, analysis populations as defined in Table 6.3-1 will be used.

Table 6.3-1: Analysis Populations

Population	Description
Enrolled	All participants who provide written (signed) informed consent.
Safety	All participants who received at least 1 dose of tracer administration.
PET	All participants who received at least 1 dose of tracer administration and have any available PET scan data.
Response-Evaluable	All participants who receive at least 1 dose of tracer administration, and:
	1) 1 evaluable whole body PET scan without major important protocol deviations in Part A (Response-Evaluable 1)
	2) At least 1 evaluable cranial PET scan in Part A or B (Response-Evaluable 2)
	3) 2 evaluable cranial PET scans in Part B (Response-Evaluable 3)
Per Protocol	All participants who receive at least 1 dose of tracer administration, and:
	1) 1 evaluable whole body PET scan without major important protocol deviations in Part A (Per-Protocol 1)
	2) At least 1 evaluable cranial PET scan without major important protocol deviations in Part A or B (Per-Protocol 2)
	3) 2 evaluable cranial PET scans without major important protocol deviations in Part B (Per-Protocol 3)

Abbreviations: PET, positron emission tomography.

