## 7.5.1 Primary Imaging Endpoints

Radiation dosimetry calculated from PET-CT images in healthy participants: As noted in Section 7.5 above, analysis of radiation dosimetry will be provided in the imaging report and is not included in the SAP.

Image acquisition window after administration of C-BMS-986196: As noted in Section 7.5 above, the determination of the image acquisition window after administration of the PET tracer will be provided in the imaging report and is not included in the SAP.

Test-retest repeatability based on standardized uptake value (SUV) of CNS PET images in participants with MS: The test-retest repeatability will be based on a quantitative analysis of cranial PET images and will be evaluated for the Response-Evaluable 3 population (Part B only). Calculated SUV (g/mL) in the brain will be summarized using descriptive statistics and will be presented by visit and for each appropriate ROI.

For each participant in the Response-Evaluable 3 population, the difference between test and retest values will be derived as well as the test-retest repeatability (%), which is defined based upon the absolute value of the difference between test and retest values normalized by their mean:

Test-retest difference = 
$$RT - T$$
,  
Test-retest repeatability (%) =  $100\% - 2 \times \left| \frac{RT - T}{RT + T} \right| \times 100\%$ ,

with T being the calculated value for the parameter measured at Visit 1 (test) and RT being the calculated value for the same parameter measured at Visit 2 (retest). Summary statistics of the test-retest difference and test-retest repeatability will be presented for each appropriate ROI.

In addition, the 95% limits of agreement for the difference will be derived for each appropriate ROI as the corresponding mean difference  $\pm 1.96$  times the standard deviation of the difference.

As sensitivity analysis, tabulation of test-retest analysis of calculated SUV may be repeated, if deemed appropriate, for the Per-Protocol 3 population (Part B only).

Test-retest repeatability based on volume of distribution ( $V_T$ ) of CNS PET images in participants with MS: The test-retest repeatability of calculated  $V_T$  (mL/cm^3) in the brain will be evaluated in the same manner as described for calculated SUV above.

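### The SAP's V_T test-retest analysis would pool any Part B pair with arterial input at one visit and venous input at the other, adding an input-function difference to tracer variability.

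*Protocol*

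**What the plan says.** **Blood sampling.** Protocol section 9.1.1.1 explains that blood samples are drawn so that the PET signal can be related to the tracer available in blood. It then adds the fallback: "If an arterial line cannot be placed, a second IV line may be placed for IV blood sampling". The sentence is not limited to a visit. Only Part C falls outside it, because no arterial lines are placed there.

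**Part B schedule.** Table 2-3 plans arterial line placement at both visits. The two tracer administrations are 2 hours to 6 days apart. For scans on one day, "the same arterial line may be used for both scans", which is an option. On matching the two scans, section 9.1.1.1 says: "In Part B, every effort must be made to perform the re-test PET scan under identical conditions as the test scan". The examples given there are the scanner and the imaging procedures. Table 2-3 asks for the same scan type at both visits and does not mention the blood input.

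**Analysis.** In SAP Table 7.5-1, V_T is a ratio to the plasma concentration, with arterial or venous left open, and SUV has no blood term. SAP section 7.5.1 computes the test-retest difference, the repeatability percentage and the 95% limits of agreement for SUV in the Response-Evaluable 3 population, and says that V_T "in the brain will be evaluated in the same manner as described for calculated SUV above". SAP Table 6.3-1 defines that population for Part B by two evaluable cranial scans, and Protocol section 5.2 asks for two scans of adequate quality. Neither sets a condition on the input function.

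**The concern.** Test-retest analysis reads the difference between two scans in one person as measurement variability. For V_T that holds only if the input function comes from the same source both times. If an arterial line is obtained at one Part B visit and not at the other, the plan permits a V_T from each source, and nothing in the SAP identifies, separates or removes the pair.

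At most 8 pairs are planned, so one such pair carries an eighth of the weight in the mean difference and can dominate the SD. Test-retest repeatability is a primary endpoint, and Protocol section 3.1 gives later use of the tracer, including dose selection, as the purpose of the study. V_T limits of agreement inflated by a change of blood source would understate how repeatable the tracer is.

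**Working it through.** The plan states no repeatability figure, SD or sample-size calculation, so there is nothing to reproduce. The check asks what the SAP's own formulas do with a mixed pair.

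**Inputs**
- From the documents: n = 8 pairs at most (Protocol section 10.2). Limits of agreement = mean difference ± 1.96 × SD. Repeatability = 100% − 2 × |RT − T| / (RT + T) × 100% (both SAP section 7.5.1).
- Assumed, because the documents give no value: a within-scan CV of 8%, so the SD of the difference is √2 × 8% = 11.3%; a venous V_T that differs from the arterial V_T by b = 5% to 30%; k = 1 or 2 mixed pairs, with the shift in the same direction.
- All differences are expressed as a percentage of mean V_T.

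**Step 1: one mixed pair with a perfectly repeatable tracer.** Put T = 1 and RT = 1 + b. The SAP repeatability is 100% − 2b/(2 + b) × 100%. For b = 20% this is 100% − 0.40/2.20 × 100% = 81.8%. For b = 5%, 10% and 30% it is 95.1%, 90.5% and 73.9%. Without the change of input it would be 100%.

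**Step 2: limits of agreement over 8 pairs.** With k shifted pairs, the expected variance of the differences is s² + b² × k(n − k) / [n(n − 1)], and the mean difference moves by bk/n. For k = 1 and n = 8 the factor is 7/56 = 1/8. With s = 11.3%, s² = 128 (in squared percentage points).

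| Mixed pairs | Shift b | Variance | SD | Half-width (1.96 × SD) | Shift in mean difference (points) |
|---|---|---|---|---|---|
| 0 | – | 128 | 11.3% | ±22.2% | 0 |
| 1 | 5% | 128 + 3.1 = 131.1 | 11.5% | ±22.4% | 0.6 |
| 1 | 10% | 128 + 12.5 = 140.5 | 11.9% | ±23.2% | 1.25 |
| 1 | 20% | 128 + 50 = 178 | 13.3% | ±26.1% | 2.5 |
| 1 | 30% | 128 + 112.5 = 240.5 | 15.5% | ±30.4% | 3.75 |
| 2 | 30% | 128 + 192.9 = 320.9 | 17.9% | ±35.1% | 7.5 |

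**Step 3: dependence on the assumed SD.** The same formula gives:
- s = 15%, one pair, b = 5%: ±29.4% becomes ±29.6%.
- s = 5%, one pair, b = 20%: ±9.8% becomes ±17.0%.
- s = 5%, two pairs, b = 20%: ±9.8% becomes ±20.6%.

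A simulation of 100,000 replicates for s = 5%, 10% and 15% agreed with the closed form. The effect runs from negligible to about a doubling, and it is larger the more repeatable the tracer is.

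**The case against.** The strongest case on the other side is that mixed pairs may be few or absent. Arterial access is planned at both Part B visits, and contraindications to an arterial line are excluded. Eligibility also requires "Documentation of normal Allen's test result at Screening and on PET scanning days in the arm that will be used for arterial line placement". Same-day scans can share a line. A mixed pair needs failure at exactly one visit, and no document reports or estimates one. This stands as a limit on likelihood. It does not supply a rule for a case that the protocol expressly permits.

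Second, the clause on identical retest conditions could be read to cover blood sampling, since its examples are not exhaustive. It remains best effort, and it governs conduct, not which pairs are analysed. The Per-Protocol 3 analysis does not fill the gap either. It is optional, and a permitted venous fallback is not in itself a protocol deviation.

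Third, the Imaging Manual, Imaging Charter or vendor imaging report may fix the input source or decide when a scan is evaluable for V_T. They were not available for this review. The SAP does not cite them for this purpose.

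Fourth, eight pairs are imprecise anyway. With 7 degrees of freedom, the 95% chi-square interval around a half-width of ±22.2% runs from 22.2 × √(7/16.01) to 22.2 × √(7/1.69), about ±15% to ±45%. The widening in Table rows for one mixed pair lies inside that range, and there is no test or decision threshold. This stands, but imprecision does not excuse a known and avoidable systematic component.

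Two stronger readings are tempting. A reader might infer that the repeatability result would measure the change of input instead of the tracer. The documents do not support that: a mixed pair contains both, only V_T is exposed, and the endpoint is worded as SUV and/or V_T. A reader might also infer that section 9.1.1.1 ranks arterial data above venous as the gold standard. That sentence follows one naming both arterial and venous lines. Protocol section 3.2.8 adds that venous quantification appears feasible on preliminary data, though without an agreement figure. The simultaneous-sampling provision, for up to 6 Part B participants during one scan, is the better evidence that interchangeability had not been assumed.

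Finally, SAP section 6 records early termination, no further Part C dosing and a synoptic report. That lowers the immediate stakes, but Part B repeatability is still to be reported.

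**Conclusion.** The gap is real and limited. Under the plan as written, a Part B pair with different blood inputs at its two visits would enter the V_T differences, repeatability percentage and limits of agreement, and no rule would identify it. SUV repeatability is not affected.

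The size cannot be fixed from the documents. With the assumed SD of 11.3%, 8 pairs and one mixed pair, a shift of 5% to 10% barely moves the limits, while 20% to 30% moves them from ±22.2% to between ±26.1% and ±30.4%. All of this rests on an assumed SD, an assumed shift and at least one mixed pair having occurred. The documents do not show that any did. The change is worth making because it is cheap and protects a primary endpoint.

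**What to change.** - Record the input type (arterial, venous or both) for each cranial scan as a flag in the transferred quantitative data.
- In SAP section 7.5.1, base the primary V_T test-retest summary and limits of agreement on Response-Evaluable 3 pairs with arterial input at both visits.
- Report any venous-venous pairs separately as a same-input set. List mixed pairs individually and do not pool them.
- Where arterial and venous samples were drawn simultaneously at one scan, use the input common to both visits.
- Keep all Response-Evaluable 3 pairs for SUV.
- If the Imaging Charter or the vendor's methods already fix the input source, cite that rule in the SAP.

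The selection should depend on input type alone and be settled before database lock, so that no pair is dropped after its V_T has been seen. The cost is one flag and a few SAP sentences. The downside is that V_T repeatability may rest on one or two fewer pairs. If no mixed or venous-only pairs occurred, nothing is lost.
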